#### *11.4.3.4 Secondary Efficacy Endpoint Analyses*

The ORR according to Investigator's assessment (cohort A and cohort B) and by independent central review (cohort B) will be presented with their associated 2-sided 95% CIs using Clopper-Pearson exact method. Discordance in ORR assessed by independent central review and by Investigator will be described.

DCR estimates will be presented in statistical tables with associated 2-sided 95% CIs.

Time-to-event endpoints (TTR, DOR, PFS and OS) will be analysed using the Kaplan-Meier method. The results will be presented for each Cohort A and B both in summary tables and graphically in Kaplan-Meier plots. Kaplan-Meier methodology will be used to characterise the

distribution of endpoints. Median durations and associated 2-sided 95% CIs will be provided. Event rates at timepoints from either first dose of study treatment or first documented response will also be estimated with associated 2-sided 95% CIs.

General censoring rules for the analysis of PFS are described below:

- Subjects who receive non-protocol anti-cancer therapy (NPACT) after start of cabozantinib and before experiencing an event will be right censored at the date of the last tumour assessment prior to the date of initiation of subsequent therapy;
- Subjects who have not experienced an event (and are not otherwise censored) at the time of data cut-off will be right censored on the date of their last tumour assessment;
- Subjects who miss two or more scheduled tumour assessments followed by an event will be right censored on the date of their most-recent tumour assessment prior to the missing assessments.

Additional supportive analyses of PFS will be defined in the SAP using alternative event definitions and censoring schemes to account for partial or completely missing assessments, address bias due to tumour assessment timing, evaluate the impact of potentially informative censoring, and to address potential discrepancies between the documentation of progression per the Investigator and per the independent central review.

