3 STATISTICAL METHODS

3.1 *Statistical analysis strategy*

The statistical analyses will be performed in accordance with International Conference on Harmonisation (ICH) E9 guideline and will be based on the pooled data from the individual study sites for each cohort separately, unless otherwise stated.

Statistical analyses will be performed by Parexel, managed by the Sponsor's biometry department.

3.1.1 *Primary efficacy endpoint*

The primary efficacy endpoint is:

SAP Final: Version 6.0: 17 August 2023

- ORR defined as the proportion of subjects with a best overall response (BOR) of a partial response (PR) or complete response (CR) at any timepoint as determined by independent central review per Response Evaluation Criteria in Solid Tumours (RECIST 1.1) in cohort A.

Details regarding the independent central review will be documented in the IRC charter finalised prior to the enrolment of the first subject.

The BOR will be derived as defined in [Appendix 1 \(1\)](#).

Below is the **definition of the estimand** used for the primary efficacy endpoint :

Treatment : Cabozantinib

Population : Subjects with unresectable, locally, advanced or metastatic RCC with a clear-cell component who progressed after prior CPI therapy with ipilimumab and nivolumab in combination (Cohort A).

Endpoint : ORR defined as the proportion of PR and CR at any timepoint during treatment period (i.e. up to 30 days after the discontinuation of Cabozantinib) as determined by independent central review per RECIST1.1.

Intercurrent events :

- Study discontinuation without response (i.e. without PR or CR) during the treatment period (composite strategy)

Subjects withdrawn from the study without response during the treatment period or subjects without any post-baseline tumour assessment are non-responders.

- Treatment discontinuation prior to RECIST 1.1 progression (treatment policy strategy)

The efficacy assessment at any timepoint prior to RECIST 1.1 progression is used regardless of whether the Cabozantinib is discontinued.

- Subjects not treated (while on treatment strategy)

Subjects will not be included in the primary efficacy analysis.

- Subjects receiving non-protocol anti-cancer treatment (while on treatment strategy)

Assessment of the response during the treatment period, i.e. until the initiation of non-protocol anti-cancer treatment.

Population-level summary : ORR compared to the historical control value of 10%.

3.1.2 *Secondary efficacy endpoints*

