Analysis based on the primary efficacy endpoint will be performed on the efficacy population in cohort A. Analyses based on the secondary efficacy endpoints will be performed on the efficacy population as defined in Section 2.1.1 and will be presented in each cohort separately. In addition, ORR and PFS according to local Investigator's review per RECIST 1.1 as well as OS will be presented in the overall population (cohort A + cohort B).

Sensitivity efficacy analyses will be based on PP population as defined in Sections 2.1.3 and 2.3. Efficacy analyses in the PP population will be presented if there is a difference greater than 15% between efficacy population and PP population. The difference will be checked for each cohort separately. In case the difference is greater than 15% for one cohort only, only this cohort will be presented in both efficacy population and PP population.

Additional supportive analysis of PFS, Kaplan-Meier and Waterfall plots will be performed only on efficacy population.

Subject data listings (Listings 16.2.6.1 to 16.2.6.8) will be based on Efficacy Population.

SAP Final: Version 6.0: 17 August 2023

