3.2.1.2 Secondary efficacy analysis

The secondary efficacy endpoints will be analysed as below.

- (a) Time-to-event endpoints such as TTR (Table 14.2.1.3 and 14.2.1.4, and Figure 14.2.1.5) will be analysed using the Kaplan-Meier method. The results will be presented for each Cohort A and B both in summary tables and graphically in Kaplan-Meier plots. Kaplan-Meier methodology will be used to characterise the distribution of endpoints. Median durations and associated 2-sided 95% CIs will be provided, as well as 25th and 75th percentiles. Event rates at timepoints will also be estimated with associated 2-sided 95% CIs.
- (b) DOR will be analysed using the Kaplan-Meier method (Tables 14.2.1.3 and 14.2.1.4, and Figure 14.2.1.6).
- (c) DCR estimates will be presented in statistical tables with associated 2-sided 95% CIs (Tables 14.2.1.3 and 14.2.1.4).
- (d) PFS will be analysed using the Kaplan-Meier method (Tables 14.2.2.1 and 14.2.2.2, and Figure 14.2.2.3).
- (e) OS will also be analysed using the Kaplan-Meier method (Tables 14.2.3.1 and 14.2.3.2, and Figure 14.2.3.3).
- (f) The ORR according to Investigator's assessment (cohort A and cohort B) and by independent central review (cohort B) will be presented with their associated 2-sided 95% CIs using Clopper-Pearson exact method (Table 14.2.4.1). TTR, DOR, DCR and PFS according to Investigator's assessment will be analysed in the same way as these endpoints assessed by independent central review (Tables 14.2.4.5 and 14.2.4.6, Figures 14.2.4.8 and 14.2.4.9, Tables 14.2.5.1 and 14.2.5.2, and Figures 14.2.5.3 and 14.2.5.4).
- (g) For the 9-item subset of disease related symptoms of the FSKI-DRS, the total score will be calculated using the number of subjects having a Baseline

SAP Final: Version 6.0: 17 August 2023

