7 APPENDICES

Appendix 1: Derived Data

The following derived data will be calculated and included in the listings:

(1) Tumour assessments and best overall response (BOR)

In case of missing tumour assessment at visit n, it should be kept missing as long as the next evaluation at visit n+1 is a Progressive Disease (PD). The best overall response (BOR) in this case is 'not evaluable' if there are no previous assessments. Otherwise, the best overall response will be assessed by using tumour assessments up to visit n-1.

On the other hand, if the assessment at visit n+1 does not show any progression, this missing assessment (at visit n) will be derived by using the assessment from previous visit n-1 (last observation carried forward method). In this case the BOR will be assessed as defined.

(2) Time-to-response (TTR)

TTR is defined as the time from start of study treatment to the date of first evidence of response (PR or CR). For subjects with no evidence of response, the TTR will be censored at the last tumour assessment and considering the censoring rules defined in the table below.

| Event | Decision | Date of event or censoring |
|--|--------------|---|
| Response to treatment (PR or CR) with no more than one missing scheduled tumor assessment before the event and without NPACT before the event. | Not censored | Earliest date between: - date of PR - date of CR |
| Response to treatment (PR or CR) with two or more missing scheduled tumor assessments before the event | Censored | Date of the last tumor assessment prior to the missing assessment. |
| Response to treatment (PR or CR) with NPACT after the start of cabozantinib and before the event | Censored | Date of the last tumor assessment prior to the date of initiation of NPACT. |
| No response (no PR and no CR) with at least one radiological or assessment after the initiation of study treatment. | Censored | Date of last radiological assessment |
| No response (no PR and no CR) without any radiological assessment after the initiation of study treatment. | Censored | Date of first cabozantinib intake |

SAP Final: Version 6.0: 17 August 2023

TTR will be calculated as:

TTR (months) = round ((date of initial response or date of last tumour assessment – date of first study drug intake +1) / (30.4375), .01)

In case of incomplete date of first study drug intake, no imputation will be used.

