Appendix 3: List of Tables, Figures and Listings (TFLs) for Final Analysis

| | |
|-----------------|---|
| Table 14.1.1 | Subject Disposition and Analysis Populations (All subjects) |
| Table 14.1.2 | Subject Disposition by Visit (All subjects) |
| Table 14.1.3 | Subject Enrolment by Country and Site (All subjects) |
| Table 14.1.4 | Sample Size of Analysis Populations by Country and Site (All subjects) |
| Table 14.1.5 | Study Exposure (Safety Population) |
| Table 14.1.6 | Study Drug Exposure (Safety Population) |
| Table 14.1.7 | Study Drug Dose Reduction, Interruption and Escalation (Safety Population) |
| Table 14.1.8 | Subject Disposition and Withdrawals (Screened Population) |
| Table 14.1.9 | Major Protocol Deviations (Safety Population) |
| Table 14.1.10 | Demographic data (Safety Population) |
| Table 14.1.11 | Renal Cell Carcinoma History (Safety Population) |
| Table 14.1.12 | Tumour Assessment by IRC – Target Lesions at Baseline (Safety Population) |
| Table 14.1.13 | Tumour Assessment by Investigator - Target Lesions at Baseline (Safety Population) |
| Table 14.1.14 | Tumour Assessment by IRC – Non-Target Lesions at Baseline (Safety Population) |
| Table 14.1.15 | Tumour Assessment by Investigator – Non-Target Lesions at Baseline (Safety Population) |
| Table 14.1.16 | Significant Medical and Surgical History (Safety Population) |
| Table 14.1.17 | Compliance (Safety Population) |
| Table 14.1.18 | Prior Medications (Safety Population) |
| Table 14.1.19 | Concomitant Medications (Safety Population) |
| Table 14.1.20 | Prior Non-Drug Therapies (Safety Population) |
| Table 14.1.21 | Concomitant Non-Drug Therapies (Safety Population) |
| Table 14.1.22 | Prior Systemic Therapies for Renal Cell Carcinoma (Safety Population) |
| Table 14.1.23 | Prior Radiotherapies for Renal Cell Carcinoma (Safety Population) |
| Table 14.1.24 | Prior Surgical Procedures for Renal Cell Carcinoma (Safety Populations) |
| Table 14.1.25 | Concomitant Surgical Procedures (Safety Population) |
| Table 14.2.1.1 | Objective Response Rate (ORR) Assessed by IRC (Efficacy Population - IRC) |
| Table 14.2.1.2 | Objective Response Rate (ORR) Assessed by IRC (Per Protocol Population - IRC) |
| Table 14.2.1.3 | Tumour Response Assessed by IRC (Efficacy Population - IRC) |
| Table 14.2.1.4 | Tumour Response Assessed by IRC (Per Protocol Population - IRC) |
| Figure 14.2.1.5 | Kaplan-Meier Plot of Time to Response (TTR) Assessed by IRC (Efficacy Population - IRC) |

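### Time to response: the partial response-date rule is worded the wrong way round, and censoring all non-responders in a Kaplan-Meier analysis calls for a responder summary and a cumulative-incidence curve beside it

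*SAP*

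**What the plan says.** **Method.** Protocol 11.4.3.4 states: "Time-to-event endpoints (TTR, DOR, PFS and OS) will be analysed using the Kaplan-Meier method". SAP 3.2.1.2 (a) follows it and adds the summaries: "Median durations and associated 2-sided 95% CIs will be provided, as well as 25th and 75th percentiles", and "Event rates at timepoints will also be estimated with associated 2-sided 95% CIs". Neither document names the timepoints for TTR.

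**Population.** SAP 3.2.1 states: "Analyses based on the secondary efficacy endpoints will be performed on the efficacy population as defined in Section 2.1.1". The final-analysis output list includes "Kaplan-Meier Plot of Time to Response (TTR) Assessed by IRC (Efficacy Population - IRC").

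**Censoring.** SAP Appendix 1 (2) states: "For subjects with no evidence of response, the TTR will be censored at the last tumour assessment". Its table sends a non-responder with no post-baseline scan to the date of first intake. Progression and death get no separate treatment. The table also censors a PR or CR that follows two or more missed scheduled scans, or that follows non-protocol anti-cancer therapy (NPACT). DOR, in Appendix 1 (3), is limited to responders; no such limit is given for TTR.

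**Contrast with ORR.** In the ORR estimand (SAP 3.1.1): "Subjects withdrawn from the study without response during the treatment period or subjects without any post-baseline tumour assessment are non-responders". The same estimand says: "The efficacy assessment at any timepoint prior to RECIST 1.1 progression is used regardless of whether the Cabozantinib is discontinued". Appendix 1 (2) has no matching limit at progression, so carrying that limit over to TTR is an inference.

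**Partial dates.** For a response with the day missing, Appendix 1 (2) takes the last day of the month and calls this conservative because it is the latest date. The next sentence substitutes first intake if first intake is *earlier* than the imputed date. The guards for TTR censoring, and for events and censoring in DOR, PFS and OS, all use *later*.

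**The concern.** There are two separate issues.

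The first is wording. A guard of this kind should stop an imputed date from falling before the start of treatment. As written, the TTR guard acts in the normal case, where treatment starts before the response. It then gives the shortest possible TTR under a rule meant to give the longest.

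The second is the estimator. Kaplan-Meier treats a censored subject as still able to respond at the rate of those who remain under scan. A subject who has progressed and left imaging, died, or never been scanned is not in that position. The risk set shrinks, later responses get too much weight, and 1-KM drifts above the proportion who have actually responded. A reader could take the TTR event rate at a late timepoint for a response rate and find that it does not agree with the ORR table. The median with all subjects in the denominator also says little about how quickly responders respond, which is what the endpoint is for.

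**Working it through.** **Design figures.** The plan states no figure for TTR. The figures that fix N and ORR reproduce: with n = 68 and rejection at 13 or more responses, the exact one-sided alpha at 10% is 0.0163 and the power at 23% is 81.6% (80% stated). 68/0.93 = 73.1, hence 74.

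**Date guard.** TTR = (response date − first intake + 1)/30.4375. Take first intake on 10 January 2021 and a response dated only April 2021.
- Month-end imputation: 30 April is 110 days after 10 January, so (110 + 1)/30.4375 = 3.65 months.
- Rule as written: 10 January is earlier than 30 April, so the response date becomes 10 January and TTR = 1/30.4375 = 0.03 months.
- With *later*: the condition is false and 3.65 months stands.

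**1-KM against cumulative incidence: one illustrative data set.** Assume 68 subjects and 16 responders (23.5%). Responses at Weeks 12/24/36/48 number 11/3/1/1. Four subjects have no post-baseline scan, and the other 48 non-responders have their last scan at those weeks in numbers 18/14/9/7. The numbers at risk are then 64, 35, 18 and 8.

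| Week | 1-KM | Cumulative incidence |
|---|---|---|
| 12 | 11/64 = 17.2% | 11/68 = 16.2% |
| 24 | 1 − (53/64)(32/35) = 24.3% | 14/68 = 20.6% |
| 36 | previous survival × 17/18: 28.5% | 15/68 = 22.1% |
| 48 | previous survival × 7/8: 37.4% | 16/68 = 23.5% |

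**Grid.** All inputs except the 23% ORR and the 12-week scan interval are assumptions. The 30% ORR is prompted by the Amendment 4 rationale, which reports more than 30% in the first 21 cohort A subjects by investigator. Responses fall 60/25/10/5% or 80/15/5% over successive scans. Median PFS in non-responders is 4, 5.5 or 7 months. The share p of progressed subjects still scanned is 0, 0.4 or 0.8. Everyone has at least one scan. At scan k (12 weeks = 2.76 months):

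at risk = remaining responders + non-responders × [S + (1 − S)p], with S = exp(−ln 2 × 2.76(k − 1)/median).

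Example with ORR 30%, 60/25/10/5, median 5.5 months, p = 0 and N = 74: at risk 74, 45.5, 29.2, 19.4; responses 13.3, 5.6, 2.2, 1.1. So 1-KM = 37.3% at Week 48, against 30%. With p = 0.4 it is 33.3%, with p = 0.8 30.9%, and with p = 1 30.0%.

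Excess of 1-KM over cumulative incidence, in points:

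| | ORR 23% | ORR 30% |
|---|---|---|
| Week 12 | 0 | 0 |
| Week 24 | 0.2–3.0 | 0.2–3.6 |
| Week 48, all p | 0.3–9.2 | 0.3–11.2 |
| Week 48, p = 0 | 1.8–9.2 | 2.3–11.2 |
| Week 48, p = 0.4 | 0.9–3.5 | 1.2–4.4 |
| Week 48, p = 0.8 | 0.3–0.9 | 0.3–1.1 |

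Of the 36 cells, 12 have a Week 48 excess below 1 point and 18 below 2. The excess is zero if p = 1 or if all responses fall at Week 12. If 5–10% of subjects are never scanned (also an assumption), it is 0.7–2.0 (ORR 23%) and 0.9–2.7 (ORR 30%) points at Week 12, and 1.5–12.5 and 1.9–15.3 at Week 48.

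**Can the order reverse?** When competing events are placed at the SAP censoring times, no: 20,000 random data sets gave no negative difference beyond rounding. When progression is dated earlier and scanning continues, yes. Take four subjects: one with stable disease censored at scan 1, two who progress at scan 1 but are scanned again at scan 2, and one response at scan 2. 1-KM has three at risk at scan 2 and gives 1/3. Aalen-Johansen has survival 1/2 after scan 1 and one subject left, and gives 1/2.

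**Median.** At a true ORR of 23%, the chance that at least 34 of 68 respond is about 1.1 × 10⁻⁶. In simulations under similar assumptions, the Kaplan-Meier curve reached 50% in 0–3% of trials at ORR 23% and in 2–19% at 30%.

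**The case against.** The protocol specifies Kaplan-Meier for TTR and the SAP follows it. ORR has its own table with an exact interval, and neither document calls a TTR event rate a response rate. All of that stands, and it makes the estimator issue one of presentation. It does not cover the censoring rule or the date guard, which exist only in the SAP.

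The figure title proves little about the analysis set, because the DOR figure carries the same population label although DOR is limited to responders. The censoring table in Appendix 1 (2) is what shows that non-responders enter the TTR curve.

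Scanning may also continue after progression: SAP 1.3.2.1 says investigator-assessed progression does not by itself end tumour assessments. This can make the excess negligible. It is not assured, because Protocol 5.2.3 requires scans only until progression in those who stopped treatment before it.

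Four stronger readings are tempting, and the documents do not support them:
- *1-KM can never lie below the cumulative incidence.* The four-subject example shows that it can in a small sample when progression is dated before the last scan.
- *The TTR event rate must exceed the reported ORR.* Appendix 1 (2) censors responders after two or more missed scans, and the ORR estimand has no such exclusion. For example, 14/66 = 21.2% against 16/68 = 23.5%.
- *Every grid cell exceeds ORR by Week 48, so the distortion is general.* By then all assumed responses have occurred, so any excess counts, and the zero-excess settings lie outside the grid.
- *The median is an artefact.* At an ORR well below 50% it will usually be not reached, which is a correct result.

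**Conclusion.** The date guard is wrong as written. It defeats its own stated aim and disagrees with the seven parallel guards. Each affected response gets a TTR of 0.03 months. How many are affected depends on how often response dates are partial, which the documents do not say.

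The estimator point is a cheap improvement. When non-responders leave imaging before later responses occur, 1-KM generally overstates the cumulative incidence of response. The size is not fixed by the documents: zero if everyone is scanned after progression or all responses come at Week 12 (with everyone scanned at least once), and otherwise about 0.3 to 11 points at Week 48 in the grid. The upper end needs no scanning after progression, and never-scanned subjects would add to it. Whether readers see the excess depends on timepoints the SAP does not name.

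A reader might infer that the efficacy conclusion is at risk. It is not: TTR is descriptive and untested, and the exact binomial test of ORR does not use it. Severity is minor.

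**What to change.** 1. In SAP Appendix 1 (2), change *earlier* to *later* in the partial response-date rule, or delete that sentence.
2. Add TTR (median, quartiles, range) among the responders counted in ORR. State that responders after missed scans are included at their documented response date, and that only responses counted in ORR are TTR events.
3. Add a cumulative-incidence curve of response with the same responders as events. The competing event is progression, death, withdrawal, start of NPACT or absence of any post-baseline scan, each without prior response. These subjects then stay in the denominator as non-responders, in line with the ORR estimand.
4. Keep the protocol-specified Kaplan-Meier output, with a note that its event rates are not response rates.
5. Record the additions in SAP section 5.

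The cost is SAP wording, one extra block in the tumour-response tables (14.2.1.3–14.2.1.4 and 14.2.4.5–14.2.4.7) and a figure beside Figures 14.2.1.5 and 14.2.4.8. No new data are needed and no planned output is lost. Protocol section 11 lets the SAP modify the planned analyses and asks for an amendment only for major changes to the primary endpoint or its analysis, so none is needed here.
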